### **Other Action Taken**

Adverse events requiring therapy must be treated with recognised standards of medical care to protect the health and well-being of the patient. Appropriate resuscitation equipment and medicines must be available to ensure the best possible treatment of an emergency situation.

If medication is administered to treat the adverse event, this medication should be entered in the Concomitant Medication Log.

### **Date of Outcome**

The date the patient recovered or died, or disease condition worsens.

### **Outcome**

The outcome of an adverse event must be classified as one of the following:

- Recovered (fully recovered or the condition has returned to the level observed at initiation of trial treatment)
- Recovered with sequelae (resulted in persistent or significant disability/incapacity)
- Recovering
- Not recovered
- Worse
- Fatal.

### **8.3 Adverse Events of Special Interest**

Adverse events of special interest include adverse events observed in earlier clinical development of TJ301 and those resulting from blocking IL-6 signaling shown by other drugs or investigational products.

Certain side effects were observed early on during the clinical development program for TJ301, including infusion-related reactions, headache, nasopharyngitis, myalgia, diarrhoea, cough, and decreased neutrophil count. In addition, certain side effects were characterized during the clinical development of other IL-6 inhibitors (e.g. tocilizumab) and have been shown to be mechanistically linked to its mode of action and its effect on inflammation. These side effects include neutropenia, thrombocytopenia, elevation of liver enzymes, lipid disorders (elevation of total cholesterol), severe infection (including tuberculosis), and gastrointestinal perforation.

### **8.4 Pregnancy and Pregnancy Outcome**

If a pregnancy occurs at any time after signing the informed consent form, the IMP should be immediately stopped and the Sponsor must be informed immediately.

Note that pregnancy itself is not an SAE, and should not be reported via the e-CRF. Contact details for the follow up on the pregnancy should be provided with the report. The Sponsor may request additional pregnancy-specific follow-up information once the pregnancy has been notified.

The mother and the foetus must be followed-up at least until the birth of the infant and one month after the birth of the infant (also pregnancy following paternal IMP exposure). In general, the follow-up will include the course; duration and the outcome of the pregnancy as well as neonatal health. If a pregnancy results in an abnormal outcome (birth defect/congenital anomaly), this must be reported as an SAE to the Sponsor according to the procedure described in Section 8.5.2. Any outcome which the Investigator and/or the Sponsor considers to be related to the IMP will be treated as an expedited report.

In cases in which a foetus may have been exposed through transmission of the IMP via semen following paternal exposure, and the pregnancy results in an abnormal outcome (birth defect/congenital anomaly) this must be reported as an SAE to the Sponsor according to the procedure described in Section 8.5.2.

## 8.5 Serious Adverse Events

### 8.5.1 Serious Adverse Event Definition

#### Serious Adverse Events during the Trial

An event is defined a serious adverse event if it:	Guidance
results in death	Any event resulting in a fatal outcome must be fully documented and reported, including deaths occurring within four weeks after the treatment ends and irrespective of the causal relationship to the IMP. The death of a patient enrolled in a trial is per se not an event, but an outcome.
is life-threatening	The term life-threatening refers to an adverse event in which the patient was at immediate risk of death at the time of the event. It does not refer to an event, which may have caused death if it were more severe.
requires in-patient hospitalisation or prolongation of existing hospitalisation	The term hospitalisation means that the patient was admitted to hospital or that existing hospitalisation was extended as a result of an event. Hospitalisation describes a period of at least 24 hours. Over-night stay for observation, stay at emergency room or treatment on an out-patient basis do not constitute a hospitalisation. However, medical judgement must always be exercised and when in doubt the case should be considered serious (i.e. if case fulfils the criterion for a medically important event). Hospitalisations for administrative or social purposes do not constitute an SAE. Hospital admissions and/or surgical operations planned before trial inclusion are not considered adverse events, if the illness or disease existed before the patient was enrolled in the trial, provided that the condition did not deteriorate during the trial.
results in persistent or significant disability/incapacity	Disability/incapacity means a substantial disruption of a person's ability to conduct normal life functions. In doubt, the decision should be left to medical

An event is defined a serious adverse event if it:	Guidance
	judgement by the Investigator.
is a congenital anomaly/birth defect	Congenital anomaly/birth defect observed in any offspring of the patient conceived during treatment with the IMP.
is an important medical event	
Important medical events are events that may not be immediately life-threatening or result in death or hospitalisation but may jeopardise the patient or may require intervention to prevent one of the other outcomes listed in the definition above. Examples of important medical events include adverse events that suggest a significant hazard, contraindication or precaution, occurrence of malignancy or development of drug dependency or drug abuse. Medical and scientific judgement should be exercised in deciding whether events qualify as medically important.
 
Important medical events include any suspected transmission of an infectious agent via a medicinal product. Any organism virus or infectious particle (e.g. prion protein transmitting Transmissible Spongiform Encephalopathy), pathogenic or non-pathogenic, is considered an infectious agent. A transmission of an infectious agent may be suspected from clinical symptoms or laboratory findings indicating an infection in a patient exposed to a medicinal product.

## 8.5.2 Collection, Recording and Reporting of Serious Adverse Events

### SAE Reporting by the Investigator

All SAEs must be reported **immediately** to the Sponsor or CRO as soon as it becomes known to the Investigator and not later than within 24 hours of their knowledge of the occurrence of the SAE. Investigators will be notified by the Sponsor or CRO of all SAEs that require prompt submission to their Institutional Review Board (IRB) or Independent Ethics Committee (IEC). Investigators should provide written documentation of IRB/IEC notification for each report to the Sponsor or CRO. The Sponsor or CRO will ensure that all SAEs are reported to the appropriate regulatory authorities.

The Investigator is responsible for submitting the completed SAE Report Form to the regulatory body with the fullest possible details **within 3 calendar days** of his/her knowledge of the SAE.

The SAE Report Form is included in the e-CRF system, and must be completed and submitted according to the instructions provided on the form. In case the e-CRF cannot be accessed and hence the SAE Report Form cannot be filled in within the e-CRF system, a paper SAE Report Form should be used and sent to the Sponsor.

The information on the form must be transferred to the e-CRF when the e-CRF is up and running again.

Completion of the Demographics, Adverse Event Log, Medical History Log and Concomitant Medication Log are mandatory for initial reports and for follow-up reports if any relevant changes have been made since the initial report. Data entries must have been made in the e-CRF for the Sponsor to access the information.

Additional information relevant to the SAE such as hospital records, results from investigations, e.g. laboratory parameters (that are not already uploaded in the e-CRF), invasive procedures, scans and x-rays, and autopsy results can be faxed or scanned and e-mailed to the Sponsor using the contact details in the section above. In any case this information must be supplied by the Investigator upon request from the Sponsor. On any copies provided, such details such as patient's name, address, and hospital ID number should be concealed and instead patient number should be provided.

The Investigator will supply the Sponsor and the IEC with any additional requested information such as results of post-mortem examinations and hospital records.

CRO contact information:

[name]

E-mail: [contact]

Sponsor contact information:

[name]

### **Expedited Reporting by the Sponsor or CRO**

The Sponsor or CRO will report all adverse events that are **serious, unexpected and with a reasonable possible causality to the IMP** as judged by either the Investigator or the Sponsor to the relevant parties within the stipulated timelines. The expectedness is assessed by the Sponsor according to the Investigator's Brochure.

SAEs will be considered reportable regardless of whether or not the IMP was used in accordance with the provisions in the protocol and the Investigator's Brochure.

## **8.6 Follow-up of Adverse Events and Serious Adverse Events**

### **8.6.1 Follow-up of Adverse Events with Onset during the Trial**

During the trial, the Investigator must follow-up on each adverse event until it is resolved or until the medical condition of the patient is stable.

After the patient's last visit, the Investigator must follow-up on any adverse event classified as serious or considered to have a reasonable possible causality to the IMP until it is resolved/recovered or until the medical condition of the patient is stable. All such relevant follow-up information must be reported to the Sponsor and CRO. If the event is a chronic condition, the Investigator and the Sponsor may agree that further follow-up is not required.

### **8.6.2 Collection of Serious Adverse Events with Onset after Last Trial Visit**

If an Investigator becomes aware of an SAE after the patient's last visit (this includes withdrawn patients, Section 4.4), and he/she assesses the SAE to have a reasonable possible causality to the IMP, the case will have to be reported to the Sponsor and CRO, using the contact information, regardless how long after the end of the trial this takes place.

## 9 STATISTICAL METHODS

All statistical analyses will be detailed in a separate Statistical Analysis Plan (SAP).

### 9.1 Determination of Sample Size

This is a proof-of-concept trial not aimed at confirming evidence of primary efficacy but rather at exploring preliminary indications of efficacy (not *per se* restricted to primary only) and safety with the aim of informing a decision about proceeding into full development. The exploratory nature of this trial requires a minimum number of patients to be exposed, yet without losing the possibility of inferring meaningful conclusions.

A sample size of N=72 (n=24 per treatment/placebo arm) patients is expected to achieve a power of 83% of detecting a trend ( $p < 0.05$ , one-sided) if the true remission rate difference (at Week 12) between the placebo and highest dose groups (600 mg Q2W) is 30% (10% for the placebo and 40% for the highest dose) using Pearson's chi-square test without continuity correction. The trial also has 70% power to reach a statistically significant result ( $p < 0.05$ , one-sided) in case the remission rate difference between placebo and treatment (300 mg Q2W and 600 mg Q2W combined together) is 20% (10% vs 30%). Considering the dropout rate of approximately 20%, a total of 90 patients will be enrolled competitively.

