### STATISTICAL METHODS

#### *Sample Size*

A sample size of N=72 (n=24 per treatment/placebo arm) patients is expected to achieve a power of 83% of detecting a trend ( $p < 0.05$ , one-sided) if the true remission rate difference (at Week 12) between the placebo and highest dose groups (600 mg Q2W) is 30% (10% for the placebo and 40% for the highest dose) using Pearson's chi-square test without continuity correction. The trial also

has 70% power to reach a statistically significant result ( $p < 0.05$ , one-sided) in case the remission rate difference between placebo and treatment (300 mg Q2W and 600 mg Q2W combined together) is 20% (10% vs 30%). Considering the dropout rate of approximately 20%, a total of 90 patients will be enrolled competitively.

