### **9.6 Endpoint Assessments**

#### **9.6.1 General Considerations**

Due to exploratory nature of this proof-of-concept trial, statistical testing will be performed both at the one-sided 20% and the one-sided 5% level. However, if the direction of the hypothesis is not self-evident, or two-sided in nature (e.g. testing for an interaction term), two-sided tests will be performed.

Quantitative variables will be described with the number of non-missing values, mean, standard deviation (SD), median, and minimum/maximum values. Qualitative variables will be described with the number and percentage of patients with each qualitative characteristic. Missing values will not be included in the calculation of percentages. All data will be listed by individual patient and study visit.

The efficacy data will be descriptively summarized and used for exploratory purposes only.

The Mayo subscores for stool frequency and rectal bleeding will be calculated as an average based on scores collected from the Patient daily Paper Diary, for up to 5, but at least 3 days prior to each applicable visit. If the patient undergoes bowel preparation for endoscopy any of the days before a visit, the day(s) should be censored from mean stool frequency and rectal bleeding subscore calculations for that visit.

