### **9.6.2 Primary Endpoint**

The primary efficacy endpoint is clinical and endoscopic remission (defined as a full Mayo score  $\leq 2$ , no individual subscore  $> 1$ , rectal bleeding subscore = 0) at Week 12 in the ITT population. This binary outcome (remission status=yes/no) variable will be analysed by a logistic regression model with treatment and the randomisation-stratification factors (prior corticosteroids treatment and consent to participate in PK substudy) as fixed effects and the baseline full Mayo score as covariate. A patient with missing data on the remission status will be assumed to be not in remission. Sensitivity analyses, using different analyses sets and missing data handling, will be detailed in the SAP.

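### The stated 83% and 70% power do not follow from the named test at N=72: uncorrected Pearson chi-square gives about 79–81% and 61–65%

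*Protocol*

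**What the plan says.** Protocol section 9.1 states that N=72, with 24 in each arm, "patients is expected to achieve a power of 83% of detecting a trend" at one-sided p<0.05 if the true Week 12 remission rates are 10% on placebo and 40% on 600 mg. The method named is Pearson's "chi-square test without continuity correction".

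The next sentence says "The trial also has 70% power to reach a statistically significant result", again at one-sided 5%, if the rates are 10% on placebo and 30% on the two doses combined. This sentence gives neither a sample size nor a test.

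The paragraph closes with the inflation: "Considering the dropout rate of approximately 20%, a total of 90 patients will be enrolled competitively". The synopsis (Sample Size) repeats the paragraph, including that the trial "has 70% power to reach a statistically significant result".

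Two other places bear on the point. Section 9.6.1 says that "statistical testing will be performed both at the one-sided 20% and the one-sided 5% level". Section 9.6.2 analyses the primary endpoint in all randomised patients: "A patient with missing data on the remission status will be assumed to be not in remission".

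**The concern.** Section 9.1 gives every input needed to check its power figures, and neither figure comes out of the test it names. They are the only numbers offered in support of the trial size. Section 9.1 also says the trial is meant to inform the decision on full development. If the pooled-dose comparison missed significance at 5%, readers would judge that against 70% power, when the named test at N=72 has 61–65%.

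A linked gap is that the dropout inflation treats dropouts as lost from the analysis, whereas section 9.6.2 keeps them in as non-remitters. Section 9.1 does not say which of these the assumed 10%, 30% and 40% describe.

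**Working it through.** **Inputs.** From section 9.1: one-sided alpha 0.05 (critical value 1.645), 24 per arm, 10% versus 40%, 10% versus 30% with doses combined, uncorrected Pearson chi-square. From section 3.1.2: 1:1:1 allocation, so the pooled comparison is 24 versus 48.

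**Formula for the named test.** Pearson's test uses the pooled variance under the null. With p̄ the weighted mean rate,

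- SE0 = √[p̄(1−p̄)(1/n1+1/n2)]
- SE1 = √[p1(1−p1)/n1 + p2(1−p2)/n2]
- power ≈ Φ[(p2−p1 − 1.645·SE0)/SE1]

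**Placebo versus 600 mg, 24 versus 24, 0.10 versus 0.40.** p̄ = 0.25, SE0 = 0.1250, SE1 = 0.1173. Power = Φ[(0.30 − 0.2056)/0.1173] = Φ(0.805) = 79.0%.

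**Placebo versus pooled doses, 24 versus 48, 0.10 versus 0.30.** p̄ = (2.4+14.4)/72 = 0.2333, SE0 = 0.1057, SE1 = 0.0901. Power = Φ[(0.20 − 0.1739)/0.0901] = Φ(0.289) = 61.4%.

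**Exact check.** Summing the binomial probabilities of every outcome pair with Pearson Z > 1.645 gives 80.5% and 65.1%.

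**Trying to reproduce 83% and 70%.** Power at N=72, one-sided 5% unless noted:

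| Method | 24 v 24 | 24 v 48 |
|---|---|---|
| Stated | 83% | 70% |
| Pearson, approximation / exact | 79.0 / 80.5% | 61.4 / 65.1% |
| Pearson, two-sided (approximation) | 68.1% | 46.8% |
| Continuity-corrected (approximation) | 67.4% | 47.7% |
| Fisher (exact) | 71.1% | 50.4% |
| Arcsine | 80.8% | 66.2% |
| Unpooled-variance z, approximation / exact | 82.0 / 82.6% | 71.7 / 70.5% |

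Of the variants tried, only the unpooled z test, Φ[(p2−p1)/SE1 − 1.645], brings both figures within 2 points: Φ(0.914) and Φ(0.574). That suggests a mismatch between the formula used and the test named, although the protocol does not say so. Renaming the test would not repair the second figure. At 24 versus 48 with 10% in both groups, the exact one-sided type I error of the unpooled test is 9.3%, against 3.8% for Pearson.

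**Reading the figures at the enrolled 90.** The inflation itself is right: 72/(1−0.20) = 90. At 30 versus 60 Pearson gives 70.9% (approximation) or 73.9% (exact). At 30 versus 30 it gives 86.6% or 88.5%, which is not 83%.

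**Group sizes at which Pearson reaches the stated powers.**

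- 83%: 26 per arm (exact, 83.6%) or 27 (approximation, 83.2%).
- 70%: 28 versus 56 (exact, 70.8%) or 30 versus 60 (approximation, 70.9%).

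**90 patients with missing counted as non-remission.** Section 9.1 does not define the assumed rates, so both cases are shown (Pearson, approximation to exact):

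- Completer rates, assuming 20% dropout in every arm. The rates become 0.8×10% = 8%, 0.8×40% = 32% and 0.8×30% = 24%. Power is 76.2–79.6% (30 versus 30) and 58.9–63.7% (30 versus 60).
- Rates that already count missing as non-remission. Power is 86.6–88.5% and 70.9–73.9%.

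**One-sided 20% level, N=72.** Pearson power is 95.2–95.6% and 89.1–89.6%.

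**The case against.** The strongest reply concerns the 70%. Its sentence names neither N nor test and speaks of the trial, which enrols 90 and analyses everyone randomised. At 30 versus 60 the usual Pearson approximation gives 70.9%, so the figure could be correct for the enrolled number. That reading cannot be excluded, and it is a good reason to attach N to each figure. It is the less natural one: the sentence is joined to the N=72 sentence by the word *also* and comes before the dropout inflation. It also cannot cover both figures, since the same basis gives 86.6–88.5% where 83% is stated.

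The first sentence speaks of a trend, so a three-arm trend test might have been meant. If the 300 mg rate is taken as 20%, which follows from 40% on 600 mg and 30% pooled, a Cochran-Armitage test gives about 80–82%. That is closer to 83%, but the sentence contrasts two groups, gives no 300 mg rate and names Pearson. It also leaves the 70% unexplained.

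The origin in an unpooled test is an inference, and the planned primary analysis is a logistic regression. The 9.3% therefore describes neither a test the protocol plans nor a fault in its error control. It only shows why relabelling the test is a poor remedy.

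The completer-versus-ITT question is separate from the arithmetic, and the completer figures depend on an assumed equal dropout. Finally, the trial is exploratory. That limits the consequence but does not make the figures right.

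**Conclusion.** The concern holds. With the test, level, rates and group sizes in section 9.1, power at N=72 is 79.0–80.5% rather than 83%, and 61.4–65.1% rather than 70%. Each range runs from the normal approximation to the exact value. The first gap is small; the pooled-dose gap is the material one. The first conclusion needs nothing beyond the stated inputs. The second rests on reading the 70% sentence as continuing at N=72 with the same test.

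The error affects what the protocol says about its power, not the validity of the planned analysis. Power at the one-sided 20% level remains about 89% or more for both comparisons. It should be corrected, but it does not call the trial size into question for an exploratory study.

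**What to change.** In section 9.1 and the synopsis:

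1. Replace 83% by about 79–81% (600 mg versus placebo, 24 versus 24) and 70% by about 61–65% (pooled doses versus placebo, 24 versus 48).
2. For each figure, name the test (uncorrected Pearson, one-sided 5%) and the group sizes, and say whether the value is exact or approximate. If the sponsor's calculation record shows that the 70% was computed at 30 versus 60, that figure should be labelled as such.
3. Add a sentence saying whether 10%, 30% and 40% are completer rates or already count missing as non-remission, with the matching power for the 90-patient ITT analysis: about 76–80% and 59–64% in the first case (20% dropout in every arm), or about 87–88% and 71–74% in the second.

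The cost is wording in two places and a less favourable stated power. Enrolment, conduct and analysis stay as they are.

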##### 3.1.2 Overall Design

This is a multicenter, stratified randomized, double-blind, placebo-controlled phase II study.

The trial includes a Run-in Period (if stable conventional treatment needed), a 4-week Screening Period, a 12-week double-blind Treatment Period, and a Safety Follow-up Period of 3 weeks to Day 105.

90 patients will be centrally, dynamically, randomly assigned to 3 groups (1:1:1) to receive 600mg TJ301 biweekly (Q2W), 300mg TJ301 Q2W or placebo Q2W. Randomisation will be stratified by prior corticosteroids treatment (yes/no) and consent to participate in PK substudy (yes/no). TJ301 or placebo administrations will occur on Days 0, 14, 28, 42, 56, and 70.

During the double-blind period and the follow-up period, patients should be on stable conventional treatment for UC.

There will be 9 ~ 10 main visits at the investigational site during the study:

- Visit 0: Run-in Period: at an optional visit (Visit 0), decision will be made if patients need stable conventional UC treatment to meet the following criteria: with corticosteroids stable for at least 2 weeks prior to Randomization at no more than 20 mg prednisone (or equivalent), and/or with medications containing 5-aminosalicylates (5-ASA) at no less than 2 g 5-ASA per day for at least 3 months and stable for at least 4 weeks prior to Randomization, and/or with azathioprine (AZA) at no less than 1.5 mg/kg/day or mercaptopurine (6-MP) at no less than 0.75 mg/kg/day for at least 6 months and stable for at least 6 weeks prior to Randomization. If patients already met the criteria, they will directly enter the Screening Period (Visit 1). If not, they will need stable conventional UC treatment during the Run-in Period except those who cannot tolerate the medications mentioned above.
- Visit 1: Screening Visit, start of Screening Period (Days -28 to -1 prior to Visit 2)
- Visit 2: Randomisation Visit (Baseline), start of 12-week Double-blind Treatment Period
- Visits 3-7: 5 visits during 12-week Double-blind Treatment Period
- Visit 8: End of Treatment (EoT) Visit, completion of 12-week Double-blind Treatment Period
- Visit 9: Safety Follow-up Visit, scheduled at 35 days after the last dose of IMP (Day 105).

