### 9.4 Analysis Sets

#### 9.4.1 Intention-to-Treat Analysis Set

The Intention-to-treat (ITT) analysis set will include all randomised patients with treatment assignment according to the planned randomisation.

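### The printed 83% and 70% power treat dropouts as leaving the analysis, but the primary analysis keeps all 90 patients and counts missing remission status as non-remission

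*Protocol*

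**What the plan says.** Protocol 9.1, repeated in the synopsis, gives two power statements at one-sided 5%.

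- 600 mg against placebo: "A sample size of N=72 (n=24 per treatment/placebo arm) patients is expected to achieve a power of 83% of detecting a trend", with remission rates of "10% for the placebo and 40% for the highest dose) using Pearson's chi-square test without continuity correction".
- Both doses combined against placebo, 10% against 30%: "The trial also has 70% power to reach a statistically significant result".

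The step from 72 to 90 is then explained in one sentence: "Considering the dropout rate of approximately 20%, a total of 90 patients will be enrolled competitively".

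Allocation is equal across the arms (3.1.2), so 90 means 30 per arm. Section 4.4 says that withdrawn patients are not replaced.

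The primary analysis in 9.6.2 is a logistic regression in the ITT population. Section 9.4.1 defines that population: "The Intention-to-treat (ITT) analysis set will include all randomised patients with treatment assignment according to the planned randomisation". Section 9.6.2 then fixes the handling of missing outcomes: "A patient with missing data on the remission status will be assumed to be not in remission". It leaves only sensitivity analyses to the SAP.

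**The concern.** Dividing 72 by 0.8 is the right inflation when patients without a Week 12 outcome are removed, so that 24 per arm remain with the assumed rates intact. Under 9.6.2 nobody is removed. All 30 per arm stay in the denominator, and those with missing status are failures. The extra patients add precision, while the imputed failures pull the arms together. These two effects need not cancel, so power computed for 72 evaluable patients does not carry over to the ITT analysis of 90.

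Section 9.1 also does not say whether its true remission rates are rates among patients with Week 12 data or rates with dropouts already counted as failures. The answer decides whether the printed power is too high or too low.

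At stake is the benchmark for the result. Section 9.1 says that the trial is to inform whether full development goes ahead. If the rates are completer rates, an ITT difference near 24 points is what the assumptions predict, yet it could be read as falling short of a 30-point target.

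**Working it through.** **Inputs.** From 9.1: 24 per arm, rates of 10%, 40% and 30%, one-sided 5% (z = 1.645), dropout 20%, 90 enrolled. From 3.1.2: equal allocation, so 30 per arm. From 9.4.1 and 9.6.2: all randomised patients, missing status = non-remission.

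**Formulas.** Let d = p2 − p1, and let p̄ be the sample-size-weighted mean rate.

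- S0 = √[p̄(1 − p̄)(1/n1 + 1/n2)]
- S1 = √[p1(1 − p1)/n1 + p2(1 − p2)/n2]
- Pooled variance (the form that matches Pearson's test): power = Φ[(d − 1.645·S0)/S1]
- Unpooled variance: power = Φ[d/S1 − 1.645]
- Exact: sum of the binomial probabilities of all outcomes in which the uncorrected Pearson z exceeds 1.645

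**Step 1: the plan's own figures.**

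- Inflation: 72/0.8 = 90, which reproduces.
- 10% v 40%, 24 v 24: p̄ = 0.25, S0 = 0.1250, S1 = 0.1173. Pooled: Φ(0.805) = 79.0%. Unpooled: Φ(0.914) = 82.0%. Exact: 80.5%.
- 10% v 30%, 24 v 48: p̄ = 0.2333, S0 = 0.1057, S1 = 0.0901. Pooled: Φ(0.289) = 61.4%. Unpooled: Φ(0.574) = 71.7%. Exact: 65.1%.

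Only the unpooled formula brings both figures within 2 points of the printed 83% and 70%.

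**Step 2: the 9.6.2 analysis, if the rates are completer rates.** Assume 20% dropout in every arm, unrelated to outcome.

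- ITT rates: 0.8 × 10% = 8%, 0.8 × 40% = 32%, 0.8 × 30% = 24%.
- Expected differences: 32 − 8 = 24 points and 24 − 8 = 16 points.
- 8% v 32%, 30 v 30: p̄ = 0.20, S0 = 0.1033, S1 = 0.0985. Pooled: Φ(0.712) = 76.2%. Unpooled: Φ(0.791) = 78.6%. Exact: 79.6%.
- 8% v 24%, 30 v 60: p̄ = 0.1867, S0 = 0.0871, S1 = 0.0741. Pooled: Φ(0.225) = 58.9%. Unpooled: Φ(0.514) = 69.6%. Exact: 63.7%.

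**Step 3: the same formulas, if the rates already count dropouts as non-remission.** The rates stay at 10%, 40% and 30%, with 30 per arm.

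| Comparison and method | Stated | 24 per arm | 30 per arm, completer rates (8/32/24%) | 30 per arm, ITT rates (10/40/30%) |
|---|---|---|---|---|
| 600 mg, pooled | 83% | 79.0% | 76.2% | 86.6% |
| 600 mg, unpooled | 83% | 82.0% | 78.6% | 88.8% |
| 600 mg, exact | 83% | 80.5% | 79.6% | 88.5% |
| Both doses, pooled | 70% | 61.4% | 58.9% | 70.9% |
| Both doses, unpooled | 70% | 71.7% | 69.6% | 79.8% |
| Both doses, exact | 70% | 65.1% | 63.7% | 73.9% |

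**Step 4: the part due to dropout handling.** This is the 24-per-arm column minus the completer-rate column, within one method.

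- 600 mg: 2.8, 3.4 and 0.9 points.
- Both doses: 2.5, 2.1 and 1.4 points.

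The remaining distance to the printed figures is already there at 24 per arm and comes from the variance formula.

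**The case against.** **Size of the loss.** A reader might subtract the completer-rate results from the printed figures and conclude that dropout handling costs up to 11 points (70 − 58.9). The documents do not support that. Most of that gap exists at 72 patients with no dropout at all, and only about 1 to 3.5 points belong to the mismatch.

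**The 70% figure.** A reader might infer that it is lost too. With the unpooled formula, which comes closest to the printed pair, it is essentially kept (69.6%). It is clearly missed only with formulas that do not give 70% at 24 v 48 either.

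**The logistic model.** Wald tests at 8% v 32% with 30 per arm give lower power still (67.8% by exact enumeration of the unadjusted test). But the same test gives only 72.0% at 10% v 40% with 24 per arm, so most of its distance from 83% reflects the choice of test. Section 9.6.2 does not specify a Wald test.

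**Reading of the rates.** Section 9.1 does not say that its rates are completer rates. If they already count dropouts as failures, power at 30 per arm exceeds both printed figures. An unconditional claim that the trial is underpowered therefore does not follow. This objection stands, but it does not rescue the text: on neither reading do 83% and 70% describe the planned analysis of 90.

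**Pattern of dropout.** Patients withdrawn for confirmed worsening (4.4) would mostly be non-remitters anyway, so the dilution may be smaller. If only half of the 20% diluted the rates (9% v 36% and 9% v 27%), power would be 81.8/84.2/84.5% and 65.1/75.0/69.0% (pooled/unpooled/exact), above the same method at 24 per arm. Unequal dropout moves power either way. By the pooled formula, 30% on placebo and 15% on active gives 84.2% and 70.7%; 10% and 25% gives 66.4% and 46.7%.

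**Importance.** The trial is exploratory. Section 9.1 also justifies its size by limiting the number of patients exposed, and 9.6.1 says that "statistical testing will be performed both at the one-sided 20% and the one-sided 5% level". At one-sided 20%, pooled-formula power at 8/32/24% is about 94% and 88%. This stands and keeps the point minor.

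**Conclusion.** The mismatch is real and lies within the protocol: 9.1 and the synopsis inflate as if dropouts were excluded, while 9.4.1 and 9.6.2 retain them as non-remitters. The printed 83% and 70% are therefore not the power of the primary analysis of 90 patients.

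The direction depends on an unstated assumption. With completer rates and equal 20% dropout unrelated to outcome, 600 mg power is below 83% by all three methods. For the pooled doses, 70% is essentially kept by the unpooled formula only. With rates that already include dropouts as failures, the inflation was unnecessary and power is higher than stated.

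The practical consequence on the completer reading is less the few points of power than the expected ITT difference, which is one fifth smaller than the one quoted. Severity is minor: the loss is modest, the trial is exploratory, and nothing here calls for a different sample size.

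**What to change.** In 9.1 and the synopsis:

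1. State whether 10%, 40% and 30% count dropouts as non-remission.
2. Replace the dropout-inflation sentence with the power at 30 randomised per arm for the ITT analysis with missing status as non-remission, and name the formula.
3. Give the ITT difference expected under the assumptions.

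Possible wording if they are completer rates: *With 30 patients randomised per arm, 20% missing Week 12 status in each arm counted as non-remission and unrelated to outcome, and remission among patients with data of 10%, 40% (600 mg) and 30% (both doses combined), the expected ITT rates are 8%, 32% and 24%. One-sided 5% power by exact enumeration of the uncorrected Pearson test is 79.6% for 600 mg against placebo (24-point difference) and 63.7% for both doses combined (16-point difference).*

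If they are ITT rates, say so, drop the inflation, and give 88.5% and 73.9% by the same method.

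Keep N=90. The cost is a reworded paragraph in two places, with no added patients, visits or procedures. The only downside is that the stated 600 mg power may become a few points less favourable. Naming the formula will also show how far the pooled-dose figure depends on it.
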